13.3 Serious Adverse Events

An AE is considered “serious” if in the opinion of the investigator it is one of the following outcomes:

- Fatal
- Life-threatening
- Constitutes a congenital anomaly or birth defect
- A medically significant condition (defined as an event that compromises subject safety or may require
- medical or surgical intervention to prevent one of the three outcomes above).
- Requires inpatient hospitalization or prolongation of existing hospitalization
- Results in persistent or significant incapacity or substantial disruption to conduct normal life functions.

13.3.1 Reporting of SAEs

All SAEs should be reported immediately to [name] M.D. at [contact] during regular business hours or at ([contact]) after hours and to the FDA. Fatal or life-threatening, unexpected adverse events will be reported to the FDA by telephone, facsimile, or in writing as soon as possible, but no later than 7 calendar days after first knowledge by the sponsor followed by as complete a report as possible within 8 additional calendar days. Serious, unexpected adverse events that are not fatal or life-threatening will be reported to the FDA by telephone, facsimile, or in writing as soon as possible, but no later than 15 calendar days after first knowledge by the sponsor.

All adverse events that are considered serious, unanticipated, and related or possibly related to the research (as defined by 21CRF312.32[a]) will be reported to the Duke University Medical Center IRB and the FDA using the appropriate SAE reporting process. At the time of the annual progress report to the Duke University Medical Center IRB and the FDA, a summary of the overall toxicity experience will be provided. Safety Oversight Committee (SOCOMM)

The Duke Cancer Institute (DCI) SOCOMM is responsible for annual data and safety monitoring of DUHS sponsor-investigator phase I and II, therapeutic interventional studies that do not have an independent data safety monitoring board (DSMB). The primary focus of the SOC is review of safety data, toxicities and new information that may affect subject safety or efficacy. Annual safety reviews includes but may not be limited to review of safety data, enrollment status, stopping rules if applicable, accrual, toxicities, reference literature, and interim analyses as provided by the sponsor-investigator. The SOC in concert with the DCI Monitoring Team (see Section 14.1 for Monitoring Team description) oversees the conduct of DUHS cancer-related, sponsor-investigator therapeutic intervention and prevention intervention studies that do not have an external monitoring plan, ensuring subject safety and that the protocol is conducted, recorded and reported in accordance with the protocol, SOPs, Good Clinical Practice (GCP), and applicable regulatory requirements.

13.4 External Data and Safety Monitoring Board

The Principal Investigator and Sub-Investigators must comply with applicable federal, state, and local regulations regarding reporting and disclosure of conflict of interest. Conflicts of interest (COI) may arise from situations in which financial or other personal considerations have the potential to compromise or bias professional judgment and objectivity. Conflicts of interest include

but are not limited to royalty or consulting fees, speaking honoraria, advisory board appointments, publicly-traded or privately-held equities, stock options, intellectual property, and gifts.

The Duke University School of Medicine's Research Integrity Office (RIO) reviews and manages research-related conflicts of interest. The Principal Investigator and Sub-Investigators must report conflicts of interest annually and within 10 days of a change in status, and when applicable, must have a documented management plan that is developed in conjunction with the Duke RIO and approved by the IRB/Institutional Ethics Committee (IEC).

Due to potential for COI in relation to proprietary interest in the pp65CMV DC vaccine, a Data Safety and Monitoring Board (DSMBplus) has been established. The Duke PRTBTC DSMBplus Charter is available upon request.

14 QUALITY CONTROL AND QUALITY ASSURANCE

14.1 Monitoring

The DCI Monitoring Team will conduct monitoring visits to ensure subject safety and to ensure that the protocol is conducted, recorded, and reported in accordance with the protocol, standard operating procedures, good clinical practice, and applicable regulatory requirements. As specified in the DCI Data and Safety Monitoring Plan, the DCI Monitoring Team will conduct routine monitoring after the third subject is enrolled, followed by annual monitoring of 1 – 3 subjects until the study is closed to enrollment and subjects are no longer receiving study interventions that are more than minimal risk.

Additional monitoring may be prompted by findings from monitoring visits, unexpected frequency of serious and/or unexpected toxicities, or other concerns and may be initiated upon request of DUHS and DCI leadership, the DCI Cancer Protocol Committee, the SOC, the sponsor, the Principal Investigator, or the IRB. All study documents must be made available upon request to the DCI Monitoring Team and other authorized regulatory authorities, including but not limited to the National Institute of Health, National Cancer Institute, and the FDA. Every reasonable effort will be made to maintain confidentiality during study monitoring.

14.2 Audits

The Duke University Office of Audit, Risk and Compliance (OARC) may conduct audits to evaluate compliance with the protocol and the principles of GCP. The PI agrees to allow the auditor(s) direct access to all relevant documents and to allocate his/her time and the time of the study team to the auditor(s) in order to discuss findings and any relevant issues.

OARC audits are designed to protect the rights and well-being of human research subjects. OARC audits may be routine or directed (for cause). Routine audits are selected based upon risk metrics generally geared towards high subject enrollment, studies with limited oversight or monitoring, Investigator initiated Investigational Drugs or Devices, federally-funded studies, high degree of risk (based upon adverse events, type of study, or vulnerable populations), Phase I studies, or studies that involve Medicare populations. Directed audits occur at the directive of the IRB or an authorized Institutional Official.

OARC audits examine research studies/clinical trials methodology, processes and systems to assess whether the research is conducted according to the protocol approved by the DUHS IRB. The primary purpose of the audit/review is to verify that the standards for safety of human subjects in clinical trials and the quality of data produced by the clinical trial research are met. The audit/review will serve as a quality assurance measure, internal to the institution. Additional goals of such audits are to detect both random and systemic errors occurring during the conduct of clinical research and to emphasize “best practices” in the research/clinical trials environment.

14.3 Data Management and Processing

14.3.1 Study Documentation

Study documentation includes but is not limited to source documents, case report forms, monitoring logs, appointment schedules, study team correspondence with sponsors or regulatory bodies/committees, and regulatory documents that can be found in the DCI-mandated “Regulatory Binder”, which includes but is not limited to signed protocol and amendments, approved and signed informed consent forms, FDA Form 1572, College of American Pathologists (CAP) and Clinical Laboratory Improvement Act (CLIA) laboratory certifications, and clinical supplies receipts and distribution records.

Source documents are original records that contain source data, which is all information in original records of clinical findings, observations, or other activities in a clinical trial necessary for the reconstruction and evaluation of the trial. Source documents include but are not limited to hospital records, clinical and office charts, laboratory notes, memoranda, subjects’ diaries or evaluation checklists, pharmacy dispensing records, recorded data from automated instruments, copies or transcriptions certified after verification as being accurate copies, microfiches, photographic negatives, microfilm or magnetic media, x-rays, subject files, and records kept at the pharmacy, at the laboratories and at medico-technical departments involved in the clinical trial. When possible, the original record should be retained as the source document. However, a photocopy is acceptable provided that it is a clear, legible, and an exact duplication of the original document.

14.3.2 Data Management

The subject’s medical records will be the primary source document for the study. Source documents include all information in original records and certified copies of original records of clinical findings, observations, or other activities in a clinical investigation used for reconstructing and evaluating the investigation.¹ Source documentations may also include paper eligibility checklists, data flowsheets, patient reported outcomes and other paper documents. The PI, study coordinator, study research nurse, data management team and all associated study key personnel, are permitted to make entries, changes, or corrections in the source documents or database per the study delegation of authority log.

Errors on the source documents will be crossed out with a single line, and this line will not obscure the original entry. Changes or corrections will be dated, signed, initialed, and explained (if necessary). Database changes will be tracked via electronic trail automatically.

¹ In 21 CFR 312.62(b), reference is made to records that are part of case histories as “supporting data;” the ICH guidance for industry *E6 Good Clinical Practice: Consolidated Guidance* (the ICH E6 guidance) (available at <http://www.fda.gov/Drugs/GuidanceComplianceRegulatoryInformation/Guidances/default.htm>) uses the term “source data/documents.” For the purpose of this guidance, these terms describe the same information and have been used interchangeably.

14.3.3 Data Management Procedures and Data Verification

The DCI Information Technology (IT) Shared Resource has developed Title 21 CFR Part 11 compliant databases for cancer clinical trials. DCI IT has extensive expertise in database quality assurance, data standards, and use of the Cancer Biomedical Informatics Grid (caBIG) tools to support cancer researchers.

Data queries will be generated automatically by the electronic case report form (eCRF) system. These data queries signify the presence of data inconsistencies. The study and data management team will cross-reference the data to verify accuracy. Missing or implausible data will be highlighted for the PI requiring appropriate responses (i.e., confirmation of data, correction of data, completion or confirmation that data is not available, etc.).

The database will be reviewed and discussed prior to database closure, and will be closed only after resolution of all remaining queries.

14.3.4 Coding

All medical terms will be coded using CTCAE (version 5).

14.3.5 Study Closure

Following completion of the studies, the PI will be responsible for ensuring the following activities:

- Data clarification and/or resolution;
- Accounting, reconciliation, and destruction/return of used and unused study drugs;
- Review of site study records for completeness;
- Shipment of all remaining laboratory samples to the designated laboratories.

15 STATISTICAL METHODS AND DATA ANALYSIS

All statistical analysis will be performed under the direction of the statistician designated in key personnel. Any data analysis carried out independently by the investigator must be approved by the statistician before publication or presentation.

15.1 Study Design Overview

This single-arm phase II study will assess the impact of tetanus pre-conditioning and adjuvant GM-CSF on overall survival of newly diagnosed GBM patients who have undergone definitive resection, are CMV+ and unmethylated, and completed standard temozolomide and radiation treatment. After completing standard of care radiotherapy with concurrent temozolomide, patients will receive 1 cycle of dose intensified TMZ followed by pp65 DC vaccination beginning on day 23.

15.2 Analysis Sets

All patients who initiate dose-intensified TMZ after completion of standard of care RT and TMZ will be included in the primary efficacy analyses, and toxicity summaries.

Subject to the availability of data, analyses of correlative objectives will include all or some of the patients who undergo vaccine 4. For analyses of migration, the first 16 patients who reach vaccine 4 will undergo migration analyses. For CCL3, all patients who reach vaccine 4 will be included in statistical analyses. For analyses of polyfunctionality, the first 24 patients who reach vaccine 4 will be considered.

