12.2 Treatment Period

All enrolled patients will then undergo a leukapheresis for generation of DCs and for baseline immunological monitoring. If the patients were part of the companion study (Pro00102797) and

have already undergone the leukapheresis procedure the relevant DCs from that study will be used for the current study and any unused vaccine products will be handled as indicated by the patient in the companion study. Within 48 hours of leukapheresis, patients will have blood samples taken for the following tests as required by the Duke Apheresis Center: CBC with auto differential, CMP, ionized Calcium, and Beta-Human Chorionic Gonadotropin (β -HCG) (for females of child-bearing potential). Total estimated blood volume required for these evaluations is 12-15 mL. For patients without sufficient venous access for leukapheresis, a temporary central intravenous catheter may be inserted. To prevent the development of hypocalcemia from the citrate used for leukapheresis, all patients will be instructed to take oral Tums, 2 tablets three times a day and at bedtime the day before and the day of the leukapheresis procedure. Patients who have lower levels of calcium will be treated per Apheresis lab standard protocols under the direction of apheresis attending physician. This first leukapheresis will be approximately a 4-hour leukapheresis, and it is estimated that 10-12 L of blood will be processed during this leukapheresis. One red top tube 10 mL draw tube will be obtained prior to leukapheresis #1 for immune monitoring. Nine yellow ACD 8.5 mL tubes and 2 red top 10 mL draw tubes will be obtained prior to leukapheresis #2.

Table 4. Schedule of Events

	CMV Screening	Main Consent ¹¹	Leukapheresis #1 ⁷	RT/TMZ	Post-RT DI TMZ Cycle 1	Td Booster & Vaccine #1	Vaccine #2	Vaccine #3	Leukapheresis #2 ⁷	Td Pre- conditioning ⁸	Vaccine #4		Vaccines #5-10	Progression ⁹
Time and Range			Within 7 weeks of resection	Within 4 (-2) weeks of RT		Day 23 (+/-2 days) Td booster given before vaccine #1	2 weeks post Vaccine #1 (+/-2 days)	2 weeks post Vaccine #2 (+/-2 days)	14 (+/-4) days after vaccine #3	3 (+/-1) week after leukapheresis #2, 12-24 hours prior to vaccine #4	3 (+/-1) week after leukapheresis #2		Every 35 (+/-7) days after previous vaccine	
CMV Screening Consent	X													
Main Consent ¹⁰		X			X									
Medical History/ Baseline Symptoms			X											
Tumor Pathology ²	X ¹													X

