Physical Exam, Neurological Exam, KPS, Vitals ³	X ¹				X	X	X	X	X	X			X	
MMSE ³					X									
MRI ⁴	X ¹				X				X				X	X
CMV IgG	X													
CBC (with auto differential) ⁵			X		X	X	X	X	X	X	X		X	
CMP ⁵			X		X	X	X	X	X	X			X	
Beta HCG quantitative (WOCBP only)			X		X				X					
Ionized Calcium			X						X					
Immune Monitoring Blood ⁶			X (1R)		X (9Y, 2R)	X (9Y, 2R)		X (9Y, 2R)	X (9Y, 2R)	X (2R)	X (9Y, 2R)		X (9Y, 2R)	X (9Y, 2R)
SOC XRT/TMZ				X										
Dendritic Cell Vaccine						X	X	X			X		X	

Con meds and AEs		X	X	X	X	X	X	X	X	X	X		X	X
------------------	--	---	---	---	---	---	---	---	---	---	---	--	---	---

¹Can be performed prior to any ICF being signed as part of standard of care evaluation.

²Patients must have a WHO Grade IV Glioma with definitive resection prior to enrollment, with residual radiographic contrast enhancement on most recent CT or MRI of <1 cm in maximal diameter in any plane. Methylation status must be checked per SOC practices (via LabCorp, CARIS, etc.) and patient must be unmethylated in order to be eligible to proceed with signing consent to undergo leukapheresis.

³Clinical evaluations with each vaccine will include a general physical examination, complete neurologic examination, KPS rating, and vitals (prior to vaccine and 30 mins post vaccine). MMSE will be performed at the Post-RT/TMZ visit only.

⁴A baseline and study eligibility MRI (with and without gadolinium enhancement) of the brain per standard of care for comparison to subsequent MRI images will also be obtained. MRI or contrasted CT, every 8 ± 4 weeks per PRTBTC standard of care (may be adjusted by the treating neuro-oncologist).

⁵CBC (with auto differential) and CMP to confirm eligibility, as per standard of care, and as per this schedule of events. Whenever blood for immune monitoring is obtained CBC with auto differential and CMP will be done to assess absolute number of T_{Regs}.

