12.6 Early Withdrawal of Subject(s)

12.6.1 Criteria for Early Withdrawal

Subjects may voluntarily withdraw from the study at any time. Subjects may be withdrawn by the PI and considered screen failures prior to vaccine therapy and the PI may also withdraw a subject from the study at any time based on his/her discretion. Reasons for PI-initiated withdrawal may include, but are not limited to the following:

- Inability to complete approximately >4 weeks of RT with TMZ as per standard of care.
- Inability to tolerate TMZ
- Patients with an active infection requiring treatment or having an unexplained febrile illness (Tmax > 99.5° F).
- Patients requiring an increase in corticosteroids, with the exception of nasal or inhaled steroid, such that at the time of first vaccination they require a dose above 2 mg of dexamethasone / day. Once vaccinations have been initiated, if patients subsequently require increased steroids, they will still be permitted to remain on the study, but every effort will be made to minimize steroid requirements.
- Adverse events
- Abnormal laboratory values
- Abnormal test procedure results (DCs fail to meet release criteria; inability to tolerate leukapheresis)
- Protocol deviation
- Administrative issues
- Disease progression
- Pregnancy

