13.2 Adverse Events of Special Interest

Adverse events will not be collected until the patient has received the DC vaccine, unless they are considered an Adverse Event of Special Interest related to the leukapheresis procedure. Only these special interest adverse events will be collected prior to the DC vaccine, all other events occurring prior to DC vaccine administration will not be recorded or monitored.

Special Interest Adverse Events that may occur during the leukapheresis procedure include:

- Allergic Reaction
- Anaphylaxis
- Pre-syncope
- Syncope
- Vasovagal reaction

Special Interest Adverse Events that may occur after the procedure, but may still be related to leukapheresis include:

- Vascular Access Complications
- Venous Injury

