15.6.5 Secondary Objective #5: Toxicity

Objective	Assess the safety of DI-TMZ treatment followed by DC vaccination.																		
Analysis Set	All patients who initiate DI-TMZ treatment.																		
Outcome	Proportion of patients with unacceptable toxicity as defined in Section 9.1.1.																		
Hypothesis	The toxicity profile associated with DI-TMZ followed by DC vaccination is safe.																		

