18-23	≥ 5																		
24-29	≥ 6																		
30-34	≥ 7																		
35-39	≥ 8																		
≥ 40	≥ 9																		

	
issued and approved by FDA. Any death attributed to trial drug, regardless of the timeline with respect to last treatment, will result in suspension of enrollment and suspension of continued treatment for enrolled subjects until review by FDA is complete and recommendations for study continuation issued and approved.

TABLE B: Probability of Accrual Suspension	
Underlying unacceptable toxicity Rate	Probability of accrual suspension
0.05	0.036
0.10	0.200
0.15	0.502
0.20	0.784
0.25	0.936
0.30	0.987

	The probability of accrual suspension as a function of the true unacceptable toxicity rate is provided in Table B. These statistics were generated assuming toxicity outcome was known at the time of accrual, and ignored issues such as time to toxicity, accrual rate, and length of follow-up. Every 6 months from the time the first patient received vaccine #1, the toxicity experienced by patients accrued to this study will be summarized and reviewed regardless of the number of patients accrued to determine whether the overall toxicity profile of treatment is unacceptable or not.
Analysis Plan	The proportion of patients who experience an unacceptable toxicity as defined in Section [9.1.1](#)
Additional Analyses	Adverse events will be summarized in several other forms to satisfy scientific and monitoring needs, as well as various regulatory reporting needs (e.g. FDA, DCI Safety Oversight Committee, and ClinicalTrials.gov). For these summaries, the frequency of adverse events will be tabulated by the maximum grade experienced.

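### Section 15 names only DI-TMZ starters as a safety set, so leukapheresis #1 reactions have no table in the patients who had the procedure

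*Combined protocol and SAP*

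**What the plan says.** **Exposure.** Section 12.2: "All enrolled patients will then undergo a leukapheresis for generation of DCs and for baseline immunological monitoring". Section 9.1 places this after resection and before radiotherapy, and allows repeats when the yield is low.

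**Collection.** Section 13.2 lists reactions such as anaphylaxis, syncope and venous injury, and adds: "Only these special interest adverse events will be collected prior to the DC vaccine". In Table 4 the row "Con meds and AEs" is marked at leukapheresis #1.

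**Withdrawal.** Section 12.6.1 introduces its list with "Reasons for PI-initiated withdrawal may include, but are not limited to the following", and one entry includes "inability to tolerate leukapheresis". Section 12.6.2 classes anyone withdrawn before DI-TMZ as an eligibility failure.

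**Analysis.** Section 15.2 states that DI-TMZ starters "will be included in the primary efficacy analyses, and toxicity summaries". The Analysis Set row of Section 15.6.5 reads "All patients who initiate DI-TMZ treatment". The Additional Analyses row of the same table, which serves FDA, oversight committee and registry reporting, says that "the frequency of adverse events will be tabulated by the maximum grade experienced". It names no set of its own.

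**Numbers.** Section 15.9 plans about 64 patients accrued and 48 starting DI-TMZ.

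**The concern.** Whether a patient is in the starter set is decided weeks after leukapheresis #1, and a bad reaction to the procedure can be the reason for never reaching DI-TMZ. A set defined that way selects on a possible consequence of the event being counted. Patients who leave early for unrelated reasons, such as progression or failure of the cells to meet release criteria, also drop out of the denominator although they had the procedure.

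What is at stake is a descriptive procedure-safety rate for an apheresis of about 4 hours, sometimes with a temporary central line. The plan collects the data for that rate but states no set of exposed patients in which to report it. The events most easily lost are those that ended participation.

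**Working it through.** **1. Which set the toxicity plan is built on.** Table B of Section 15.6.5 gives suspension probabilities for true toxicity rates 0.05 to 0.30. An exact binomial recursion over the Table A boundaries, checked after each patient, gives:

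| True rate | Table B | N = 48 | N = 64 |
|---|---|---|---|
| 0.05 | 0.036 | 0.036 | 0.039 |
| 0.10 | 0.200 | 0.198 | 0.283 |
| 0.15 | 0.502 | 0.496 | 0.701 |
| 0.20 | 0.784 | 0.779 | 0.933 |
| 0.25 | 0.936 | 0.933 | 0.991 |
| 0.30 | 0.987 | 0.986 | 0.999 |

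N = 48 reproduces the table to within one percentage point; N = 64 does not. The stopping rule therefore rests on the DI-TMZ starters, consistent with the stated set. This confirms the set in use. It does not itself show a fault.

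**2. Share of planned accrual outside that set.** 64 - 48 = 16, and 16/64 = 25%, for all reasons together.

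**3. Effect on a leukapheresis #1 rate.** Let R patients have a reaction and let a share w of them leave before DI-TMZ. The documents give neither number.

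- Starter-set rate = R(1 - w)/48
- Exposed-set rate = R/64
- Ratio = (1 - w) × 64/48

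| w | 0 | 0.25 | 0.50 | 0.75 | 1 |
|---|---|---|---|---|---|
| Ratio | 1.33 | 1.00 | 0.67 | 0.33 | 0 |

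The break-even is w = 1 - 48/64 = 25%. Above it the tabulated rate is too low; below it, too high.

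**4. Illustration with R = 4 (assumed), exact 95% intervals.** The exposed-set rate is 4/64 = 6.3% (1.7 to 15.2%).

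| Reactors leaving before DI-TMZ | Starter-set rate | 95% interval |
|---|---|---|
| 0 | 4/48 = 8.3% | 2.3 to 20.0% |
| 1 | 3/48 = 6.3% | 1.3 to 17.2% |
| 2 | 2/48 = 4.2% | 0.5 to 14.3% |
| 4 | 0/48 = 0% | 0 to 7.4% |

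**5. The exposed number may be below 64.** Footnote 10 of Table 4 lets some patients have leukapheresis under Pro00102797 before the main consent of this trial. Suppose m of the 48 starters did so and have no leukapheresis #1 events recorded here (assumption). The exposed set is then 64 - m and the break-even is 1 - 48/(64 - m): 25% at m = 0, 14.3% at m = 8 and 0% at m = 16.

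**The case against.** The strongest reply is that the exclusion is inferred. Section 15.2 says who is included and does not say that nobody else is. The Additional Analyses row of Section 15.6.5 promises adverse event summaries in further formats and ties them to no set, so a statistician could use a wider one. This stands as a limit. A reader might infer that the plan definitely drops these patients, and the documents do not go that far. They permit a wider set but never name one.

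No objective or endpoint concerns a leukapheresis reaction rate, and leukapheresis is not among the interventions to which Section 13.1 attributes events. The starter set is right for the Section 15.6.5 objective, which concerns DI-TMZ followed by vaccination. This too stands, and it confines the point to descriptive reporting.

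The events are also recorded elsewhere: the running summary in Section 13.1.1, and the serious event reports and annual toxicity summary in Section 13.3.1. That is correct, but none of these defines an exposed denominator. The parallel summary in Section 9.1.3 covers only events after RT/TMZ.

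Finally, withdrawal for intolerance is discretionary and is absent from the withdraw-and-replace reasons in Section 9.1. If reactors leave at the same 25% as everyone else, the ratio is 1.00. A reader might infer that the plan understates procedure risk. The documents give no attrition among reactors, so neither direction is supported.

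**Conclusion.** The point holds as a minor one. DI-TMZ starters are the only set that Section 15 states for toxicity. Applied as written to the adverse event tables, that set leaves out leukapheresis #1 reactions in patients who leave before DI-TMZ and uses about 48 instead of up to about 64 as the denominator.

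The size and direction of any bias are unknown, and the number of patients involved is probably small. The 64 and 48 are planned figures; R, w and m are assumptions, and the illustrative intervals overlap widely. The calculation covers leukapheresis #1 only, since leukapheresis #2 follows vaccine 3 and those patients are already starters.

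A reader might take this as a flaw in the trial's safety assessment at large. It is not: the unacceptable-toxicity endpoint, the stopping rule and the primary survival analysis are unaffected.

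**What to change.** In Section 15.2 and in the Additional Analyses row of Section 15.6.5, add a procedure-safety set: all patients who start at least one leukapheresis under this protocol, whether or not they later start DI-TMZ. Tabulate the Section 13.2 events in that set by patient, with the number leading to withdrawal. Keep the DI-TMZ-starter set for treatment toxicity and the stopping rule.

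The cost is a sentence defining the set and one extra table, from data that Section 13.2 already requires. The reported leukapheresis rate may move up or down as a result. Breakdowns by procedure, or separate rows for leukaphereses done under Pro00102797, are optional.
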